#### **12.2 Study Termination**

The Sponsor or designee reserves the right to terminate the study. The Investigator reserves the right to terminate their participation in the study, according to the terms of the site contract. The Investigator/Sponsor or designee should notify the IEC/IRB in writing of the trial's completion or ET. An Investigator who terminates participate is required to send a copy of the IEC/IRB notification to the Sponsor or designee.

#### **12.3 Study Documentation and Storage**

Source documents are original documents, data, and records from which the patient's case report form data are obtained. These include but are not limited to hospital records, clinical and office charts, laboratory and pharmacy records, diaries, imaging, and correspondence. In this study, eCRF may not be used as source documents.

The Investigator and Study Center staff are responsible for maintaining a comprehensive and centralized filing system of all study-related (essential) documentation in accordance with Section 8 of the ICH Guidelines (E6), suitable for inspection at any time by representatives from the Sponsor or designee and/or applicable regulatory authorities. Elements should include:

- Patient files containing completed case report forms, informed consents, and supporting copies of source documentation
- Study files containing the protocol with all amendments, Investigator's Brochure, copies of pre-study documentation and all correspondence to and from the IEC/IRB and the Sponsor or designee
- If drug supplies are maintained at the Study Center, proof of receipt, Study Drug Product Accountability Record, Return of Study Drug Product for Destruction, final Study Drug product reconciliation, and all drug-related correspondence

In addition, all original source documents supporting entries in the case report forms must be maintained and be readily available for the duration required by GCP or local regulatory requirements, whichever is longer.

No study document should be destroyed without prior written agreement between the Sponsor or designee and the Investigator. Should the Investigator wish to assign the study records to another party or move them to another location, he/she must notify the Sponsor or designee, in accordance with GCP.

#### **12.4 Study Monitoring**

The Sponsor representative and regulatory authority inspectors are responsible for contacting and visiting the Investigator for the purpose of inspecting the facilities and, upon request, inspecting the various records of the trial (e.g., case report forms and other pertinent data) provided that patient confidentiality is respected.

The Sponsor monitor or designee is responsible for inspecting the case report forms at regular intervals throughout the study to verify adherence to the protocol; completeness, accuracy, and consistency of the data; and adherence to local regulations on the conduct of clinical research. The monitor should have access to patient medical records and other study-related records needed to verify the entries on the case report forms. Source data should be attributable, legible, contemporaneous, original, and accurate (ALCOA) and must meet the regulatory requirements for recordkeeping.

The Investigator agrees to cooperate with the monitor to ensure that any problems detected in the course of these monitoring visits, including delays in completing case report forms, are resolved.

In accordance with ICH GCP and the Sponsor's audit plans, this study may be selected for audit by representatives from the Sponsor's Clinical Quality Assurance Department (or designees). Inspection of Study Center facilities (e.g., pharmacy, drug storage areas, laboratories) and review of study-related records will occur to evaluate the trial conduct and compliance with the protocol, ICH GCP, and applicable regulatory requirements.

To ensure the quality of clinical data a clinical data management review will be performed on patient data received by the Sponsor or designee. During this review, patient data will be checked for consistency,

omissions, and any apparent discrepancies. In addition, the data will be reviewed for adherence to the protocol and GCP. To resolve any questions arising from the clinical data management review process, data queries and/or Study Center notifications will be sent to the Study Center for completion and return to Sponsor or designee.

The Principal Investigator will sign and date the indicated places on the case report form. These signatures will indicate that the Principal Investigator inspected or reviewed the data on the case report form, the data queries, and the Study Center notifications, and agrees with the content in accordance with the general investigational plan.

### **12.5 Language**

Case report forms must be completed in English. Whenever possible, the trade name rather than the generic name for concomitant medications should be recorded and if possible, in English. Generic names are acceptable if the trade name is unknown. Combination medications should be recorded using their trade name in English if possible.

All written information and other material to be used by patients and investigative staff must use vocabulary and language that are clearly understood.

### **12.6 Compensation for Injury**

The Sponsor maintains appropriate insurance coverage for clinical trials and will follow applicable local compensation laws. Patients will be treated and/or compensated for any study-related illness/injury in accordance with the information provided in the Compensation for Injury section of the Informed Consent document.

**14. APPENDICES**

## **Appendix A     Schedule of Procedures**

[Schedule of Procedures for Weekly and Every 2-Week Dosing Cohorts](#)

[Schedule of Procedures for Every 4-Week Dosing Cohorts](#)

**Appendix A Schedule of Procedures – Weekly and Every 2-Week Dosing**

	Screen	Treatment Period																		Follow-up Period			
Study Week	-4 to -1	1	1	5	9	13	17	21	25	27 P			29	33	37	41	45	49	53/ET	4*	10*	16*	
Study Day	-28 to -1	1	2 a	29	57	85	113	141	169	183	184 a	185 a	197	225	253	281	309	337	365	*Post Treatment Period			
Visit and Testing Window +/- Days	0	-3 b	0	2	2	2	3	3	3	3	0	0	3	3	3	3	3	3	3	3	3	3	
Informed Consent	X																						
Outpatient Visit	X	X	X	X	X	X	X	X	X	X	X	X	X	X	X	X	X	X	X	X	X	X	X
Inclusion/Exclusion Criteria	X	X																					
Medical History c	X																						
Vital Signs	X	X		X	X	X	X	X	X	X			X	X	X	X	X	X	X	X	X	X	X
Physical Examination	X	X		X		X		X		X				X		X		X	X	X	X	X	X
Body Weight and Height d	X									X						X							X
12- lead ECG (triplicate)	X	X		X		X		X		X				X		X		X	X	X	X	X	X
24-Hour Urine for Creatinine Clearance and Protein	X																						
Extended Urinalysis e	X	EXTENDED URINALYSIS PERFORMED EVERY 14 DAYS e, f																		X	X	X	
Renal Biomarkers g	X	RENAL BIOMARKERS PERFORMED EVERY 14 DAYS f, g																		X h	X h	X h	
Serum Creatinine and Cys-C i, j		SERUM CREATININE and Cys-C PERFORMED EVERY 14 DAYS f, i																		X	X	X	
Genetic Testing (optional)		X																					
Chemistry Panel j, k	X	EVERY 14 DAYS f			X	X	X	X					X	X	X	X	X	X	X	X	X	X	X
Hematology j, k	X	HEMATOLOGY PERFORMED EVERY 14 DAYS f, k																		X h	X h	X h	
Platelet Function		X		X	X	X	X	X	X	X			X	X	X	X	X	X	X	X	X	X	X
Coagulation	X	X								X													
Hepatitis B, C, HIV	X																						
Thyroid Panel	X																						
hsCRP		X								X									X				X
Plasma PK - ISIS 681257 l		X 	X 	X	X	X	X	X	X	X 	X 	X 	X		X				X	X	X	X	X
ISIS 681257 Antibodies		X		X	X	X				X									X				X

**Appendix A Schedule of Procedures – Weekly and Every 2-Week Dosing *Continued***

Study Week	Screen	Treatment Period																	Follow-up Period			
	-4 to -1	1	1	5	9	13	17	21	25	27 p			29	33	37	41	45	49	53/ET	4*	10*	16*
Study Day	-28 to -1	1	2 a	29	57	85	113	141	169	183	184 a	185 a	197	225	253	281	309	337	365	*Post Treatment Period		
Visit and Testing Window +/- Days	0	-3 b	0	2	2	2	3	3	3	3	0	0	3	3	3	3	3	3	3	3	3	3
FSH (women only, if applicable) i, m	X																					
Serum Pregnancy Test m	X	X		X	X	X	X	X	X				X	X	X	X	X	X	X	X	X	X
Archived Serum & Plasma Samples i, n		X			X		X			X					X		X		X	X	X	X
PD Panel j	X	X		X	X	X	X	X		X			X		X		X		X	X	X	X
Lipid Panel j	X	X		X	X	X	X	X		X			X		X		X		X	X	X	X
Lp(a) Characterization		X																				
Study Drug: SC Injection		WEEKLY SUBCUTANEOUS ADMINISTRATION OF STUDY DRUG (Week 1 through Week 52/Day 358) o EVERY 2-WEEK SUBCUTANEOUS ADMINISTRATION OF STUDY DRUG (Week 1 through Week 51/Day 351) o																				
Adverse Events	X	X	X	X	X	X	X	X	X	X	X	X	X	X	X	X	X	X	X	X	X	X
Concomitant Medication	X	X	X	X	X	X	X	X	X	X	X	X	X	X	X	X	X	X	X	X	X	X

All procedures and study samples are to be done pre-dose at respective visits, unless specified

- a Visit only required for patients in PK subgroup.
- b Day 1/Baseline assessments can be performed up to 3 days (-3 days) prior to the actual Day 1 visit, which is the day of first Study Drug dose.
- c Patient charts will be reviewed in order to collect disease associated medical history data such as CVD history.
- d Height only required at Screening.
- e All tests listed in [Appendix B](#) under Extended Urinalysis should be performed, including routine urinalysis, urine microscopy, UACR and UPCR.
- f Assessments and procedures to be conducted by either a home healthcare service or the Study Center. Patient Study Center visits must be no more than 4 weeks apart during the treatment period.
- g Urine samples for renal biomarkers will be collected. Sample analysis will be conducted in accordance with Safety Monitoring for Renal Function ([Section 8.5.2](#)).
- h During follow-up period, hematology sampling for platelet values and urine renal biomarker samples are taken every 14 days for 6 weeks post treatment period, then at Week 10 and Week 16 Follow-up visits.
- i Serum Creatinine and Cys-C will be collected as a part of chemistry panel at visits when chemistry panel is performed, or as stand-alone samples at time points when a chemistry panel is not performed.

### Appendix A Schedule of Procedures – Weekly and Every 2 Week Dosing Continued

- j Blood samples to be collected after an overnight fast of at least 10 hours and preferably not more than 12 hours, unless tests are repeated for safety reasons.
- k If the platelet value, serum creatinine or liver enzyme tests are uninterpretable (e.g., due to clumping, hemolysis or quantity not sufficient) a repeat blood specimen should be re-drawn as soon as possible (ideally within 7 days). All platelet count results will be reviewed promptly (within 24 hours of receipt) by the Investigator as per [Section 6.2.1](#). Any case of a platelet count  $< 50,000/\text{mm}^3$  should be reported in an expedited fashion to the Sponsor.
- l Refer to [Appendix C](#) for PK Sampling schedule.
- m Women who are not surgically sterile or post-menopausal.
- n Serum and plasma samples will be collected and stored for follow-up exploration of laboratory findings and/or AEs (e.g., measurement of cytokine and/or chemokine levels, measurement of additional markers of kidney function, measurement of antibodies, etc.) and will be retained until completion of the final study report.
- o Patients will continue treatment in the study for 12 months, or until the last patient reaches 6 months of exposure. When this milestone is met, all patients still on treatment will have an End of Treatment visit, then enter a 16-week post-treatment follow-up period.
- p For the last patient to reach 6 months of exposure ONLY, the Week 27 visit will count as the End of Treatment Visit, therefore all Week 53/ET assessments will be included in this visit. No dose will be administered at this visit.

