#### **5.1 Inclusion Criteria**

1. Must have given written informed consent (signed and dated) and any authorizations required by local law and be able to comply with all study requirements
2. Males or females aged  $\geq 18$  and  $\leq 80$  years old at the time of informed consent
3. Clinical diagnosis of CVD defined as documented coronary artery disease (CAD), stroke, or peripheral artery disease
4. Lp(a) plasma level  $\geq 60$  mg/dL
5. Must be on standard-of-care preventative therapy for other than elevated Lp(a) CVD risk factors
6. Patients on the following medications must be on a stable regimen for at least 4 weeks prior to Screening and expected to remain on a stable regimen through the end of the post-treatment follow-up period:
  - a. lipid lowering drugs (statins, ezetimibe, proprotein convertase subtilisin/kexin type 9 [PCSK9s] inhibitors, niacin, fibrates, fish oil or other products containing omega-3 fatty acids including OTC preparations)
  - b. antiplatelet drugs
  - c. testosterone, estrogens, progesterone, growth hormone or progestins
7. Females: must be non-pregnant and non-lactating and either:

- a. surgically sterile (e.g., tubal occlusion, hysterectomy, bilateral salpingectomy, bilateral oophorectomy)
- b. post-menopausal (defined as 12 months of spontaneous amenorrhea in females > 55 years of age or, in females ≤ 55 years, 12 months of spontaneous amenorrhea without an alternative medical cause and FSH levels in the postmenopausal range for the laboratory involved)
- c. Abstinent\* or
- d. if engaged in sexual relations of child-bearing potential, agree to use 2 highly effective contraceptive methods (refer to [Section 6.3.1](#)) from the time of signing the informed consent form until at least 16 weeks after the last dose of Study Drug (ISIS 681257 or placebo)

\* Abstinence is only acceptable as true abstinence, i.e., when this is in line with the preferred and usual lifestyle of the patient. Periodic abstinence (e.g., calendar, ovulation, symptothermal, post-ovulation methods), declaration of abstinence for the duration of a trial and withdrawal are not acceptable methods of contraception

8. Males must be surgically sterile or, if engaged in sexual relations with a female of child-bearing potential, the patient must be using an acceptable contraceptive method (refer to [Section 6.3.1](#)) from the time of signing the informed consent form until at least 16 weeks after the last dose of ISIS 681257

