### 6.3 Restriction on the Lifestyle of Patients

#### 6.3.1 Contraception Requirements

All male patients and women of childbearing potential must refrain from sperm/egg donation and either be abstinent† or practice effective contraception from the time of signing the informed consent form until at least 16 weeks after their last dose of study treatment.

Male patients engaged in sexual relations with a female of child-bearing potential must also encourage their female partner to use effective contraception from the time of signing the informed consent until 16 weeks after the patient's last dose of study treatment.

For the purposes of this study, women of childbearing potential are defined as any female who has experienced menarche, and who does not meet 1 of the following conditions:

- Postmenopausal: 12 months of spontaneous amenorrhea in females > 55 years of age or, in females ≤ 55 years, 12 months of spontaneous amenorrhea without an alternative medical cause and FSH levels in the postmenopausal range for the laboratory involved
- 6 weeks after surgical bilateral oophorectomy with or without hysterectomy
- Post hysterectomy

For the purposes of the study, effective contraception is defined as follows:

For male patients:

- Effective male contraception includes a vasectomy with negative semen analysis at Follow-up, or the use of condoms together with spermicidal foam/gel/film/ cream/suppository
- Male patients with partners that are pregnant must use condoms as contraception to ensure that the fetus is not exposed to the Study Drug

For female patients and female partners of male patients:

- Using 2 of the following acceptable methods of contraception: surgical sterilization (e.g., bilateral tubal ligation), hormonal contraception, intrauterine contraception/device, or any 2 barrier methods (a combination of male or female condom\* with diaphragm, sponge, or cervical cap) together with spermicidal foam/gel/film/cream/suppository

†**Note:** Abstinance is only acceptable as true abstinence, i.e., when this is in line with the preferred and usual lifestyle of the patient. Periodic abstinence (e.g., calendar, ovulation, symptothermal, post-ovulation methods), declaration of abstinence for the duration of a trial and withdrawal are not acceptable methods of contraception.

**\*Note: A female condom and a male condom should not be used together as friction between the 2 can result in either or both products failing.**

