### 8.8 Discontinuation of Study Drug

A patient must permanently discontinue study treatment for any of the following:

- The patient becomes pregnant. Report the pregnancy according to instructions in [Section 9.5.4](#)
- The patient withdraws consent
- The patient experiences an AE that necessitates permanent discontinuation of Study Drug
- The patient develops laboratory test abnormalities that meet any of the stopping rules listed in [Sections 8.6.1](#) to [8.6.3](#)
- When a platelet count of less than  $50,000/\text{mm}^3$ , or a platelet count less than  $75,000/\text{mm}^3$  while the patient is on a reduced dose.

The reason for discontinuation of Study Drug must be recorded in the electronic Case Report Form (eCRF) and source documentation.

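### Footnote m in both Appendix A schedules leaves premenopausal women with only a tubal procedure without scheduled pregnancy tests from Day 1, although Section 6.3.1 counts them as of childbearing potential

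*Protocol*

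**What the plan says.** In Appendix A, both the weekly/every 2-week schedule and the every 4-week schedule have a "Serum Pregnancy Test" row marked with footnote m. In both, the footnote restricts the row to "Women who are not surgically sterile or post-menopausal". The same footnote is attached to the FSH row.

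For women, surgical sterility is spelled out only in inclusion criterion 7a (Section 5.1, repeated in the Synopsis): "surgically sterile (e.g., tubal occlusion, hysterectomy, bilateral salpingectomy, bilateral oophorectomy".

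Section 6.3.1 sets the class differently. There, "women of childbearing potential are defined as any female who has experienced menarche, and who does not meet 1 of the following conditions". The conditions are post-menopausal status, "6 weeks after surgical bilateral oophorectomy with or without hysterectomy", and hysterectomy. No tubal procedure is among them. Tubal ligation appears further down, in the contraception rule for female patients and female partners: "Using 2 of the following acceptable methods of contraception: surgical sterilization (e.g., bilateral tubal ligation".

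Section 8.8 makes pregnancy a reason for permanent discontinuation, in the entry beginning "The patient becomes pregnant. Report the pregnancy according to instructions in". Section 9.5.4 provides for a test when pregnancy is suspected, follow-up included. Appendix B lists a serum hCG for women among the screening tests, without footnote m's limit.

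**The concern.** The scheduled serum tests are the protocol's means of finding a pregnancy that nobody suspects, in a trial where a confirmed pregnancy ends dosing for good. They should cover everyone the protocol itself regards as able to become pregnant. Footnote m follows the wording of criterion 7a instead, so it drops a group that Section 6.3.1 keeps in that class.

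The protocol does not elsewhere waive testing because pregnancy is unlikely. Women admitted as abstinent under criterion 7c are neither surgically sterile nor post-menopausal, so they are tested throughout. A woman with a tubal procedure, from whom Section 6.3.1 asks a second method or abstinence, is not. What is at stake is participant safety and internal consistency, not the efficacy analysis.

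**Working it through.** The plan states no figure to reproduce. The check compares definitions and then counts visits.

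**Step 1: each category under the three texts.**

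| Woman | Criterion 7a/7b | Section 6.3.1 | Footnote m |
|---|---|---|---|
| Post-menopausal | admitted under 7b | not of childbearing potential | not tested |
| Hysterectomy | surgically sterile | not of childbearing potential | not tested |
| Bilateral oophorectomy, at least 6 weeks earlier | surgically sterile | not of childbearing potential | not tested |
| Premenopausal, tubal procedure only | surgically sterile | **of childbearing potential** | **not tested** |
| Premenopausal, no such surgery (7c or 7d) | not surgically sterile | of childbearing potential | tested |

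The texts agree in every row except the fourth. That row depends on reading surgically sterile in footnote m as criterion 7a does. No other definition is offered, and Section 6.3.1 itself calls tubal ligation surgical sterilization.

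**Step 2: tests missed over a full course.** From the pregnancy test row, identical in both schedules:

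- Days 1, 29, 57, 85, 113, 141, 169: 7 tests
- Days 197, 225, 253, 281, 309, 337, 365: 7 tests
- Follow-up Weeks 4, 10 and 16: 3 tests
- Total from Day 1: 7 + 7 + 3 = 17

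Screening would make 18. It is left out because Appendix B lists the screening hCG for women without qualification. This gives the plan the benefit of the doubt, since footnote m is attached to the screening entry as well.

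**Step 3: time without a scheduled test.** Day 1 to Day 365 is (365 − 1)/7 = 52 weeks. Adding 16 weeks of follow-up gives 52 + 16 = 68 weeks. Treatment may end earlier for patients enrolled late, so 17 tests and 68 weeks are full-course figures and shorter courses lose fewer.

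**Step 4: would restoring the tests need new visits or draws?** The on-treatment tests are 28 days apart, and 28 = 2 × 14, so each falls on the 14-day grid for hematology and for serum creatinine and cystatin C. The three follow-up visits also list both. All 17 time points are outpatient visits, so blood is already being drawn at each one.

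**The case against.** The best counter-argument is that footnote m agrees with criterion 7a, so the odd text out is Section 6.3.1. That section governs contraception, and not testing women with a permanent procedure could be deliberate. The inconsistency could then be removed by adding tubal procedures to the exemptions in Section 6.3.1, with no added tests. It is true that no sentence says Section 6.3.1 decides who is tested. But that repair would drop the second method the protocol now requires of women with tubal ligation. It would loosen an existing precaution to match a footnote.

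It is also fair that other safeguards remain. Section 9.5.4 requires a suspected pregnancy to be reported immediately and tested, site visits on treatment are at most four weeks apart, and adverse events are reviewed at each visit. These reduce the risk. They do not replace a scheduled test, which serves to find a pregnancy before it is suspected.

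Stronger readings that a reader might infer, and that the documents do not support:

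- **She is released from contraception.** Section 6.3.1 binds her from consent, criterion 1 requires that she "be able to comply with all study requirements", and Section 9.5.4 repeats the duty. On contraception, only the wording of criterion 7a is out of step.
- **She is never tested.** The screening hCG in Appendix B carries no such limit.
- **A known number of women is exposed.** The protocol gives no count. In a population with established cardiovascular disease the group is probably small, and zero is possible.
- **Footnote p gives a minimum number of missed tests.** It applies only to the last patient to reach 6 months, so it supplies no general lower figure.
- **Criterion 7a must be rewritten.** The gap lies in the footnote and can be closed there.

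**Conclusion.** The point holds as a gap in scheduled safety testing. A premenopausal woman with only a tubal procedure misses 17 scheduled serum pregnancy tests over the 68 weeks from Day 1 of a full course, while Section 6.3.1 classes her as of childbearing potential. After screening, detection rests on suspicion.

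The conclusion rests on two readings: that surgically sterile in footnote m means what criterion 7a says, and that the screening hCG in Appendix B is done in all women. If the second fails, she misses 18 tests.

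The practical extent is limited. The number of such women is unknown and may be nil, contraception duties stand, and no efficacy endpoint, power figure or analysis is touched. It should still be corrected, because the remedy is small and precise.

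**What to change.** In both Appendix A schedules, detach footnote m from the serum pregnancy test row and give that row its own footnote: *women of childbearing potential as defined in Section 6.3.1*. Keep footnote m for the FSH row.

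The cost is up to 17 additional serum assays per affected woman, run on blood drawn at visits that already take place, so no visit or venepuncture is added. The footnote change needs a protocol amendment with the regulatory and ethics committee steps of Section 12.1. It adds no contraception duty.

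Rewording criterion 7a (Section 5.1 and Synopsis) to match Section 6.3.1 would tidy the terminology. It is optional: it alters an eligibility criterion, is debatable for bilateral salpingectomy, and is not needed to close the testing gap.
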